#### **5.4.1. Liver Chemistry Stopping Criteria**

**Liver chemistry stopping and increased monitoring criteria** have been designed to assure subject safety and evaluate liver event etiology (in alignment with the Food and Drug Administration (FDA) premarketing clinical liver safety guidance).

<http://www.fda.gov/downloads/Drugs/GuidanceComplianceRegulatoryInformation/Guidances/UCM174090.pdf>

Liver Safety Required Actions and Follow up Assessments Section can be found in [Appendix 2](#).

##### **5.4.1.1. Study Treatment Restart or Rechallenge**

Study treatment restart or rechallenge after liver chemistry stopping criteria are met by any subject participating in this study is not allowed.

#### **5.4.2. QTc Stopping Criteria**

- The *same* QT correction formula *must* be used for *each individual subject* to determine eligibility for and discontinuation from the study. This formula may not be changed or substituted once the subject has been enrolled.
  - For example, if a subject is eligible for the protocol based on QTcB, then QTcB must be used for discontinuation of this individual subject as well.
  - Once the QT correction formula has been chosen for a subject's eligibility, the *same formula* must continue to be used for that subject *for all QTc data being collected for data analysis*. Safety ECGs and other non-protocol specified ECGs are an exception.
- The QTc should be based on single or averaged QTc values of triplicate electrocardiograms obtained over a brief (e.g., 5-10 minute) recording period.

A subject who meets either of the bulleted criteria below will be withdrawn from the study:

- QTc > 500 msec OR Uncorrected QT > 600 msec

- Change from baseline of QTc > 60 msec

For subjects with underlying **bundle branch block**, follow the discontinuation criteria listed below:

Baseline QTc with Bundle Branch Block	Discontinuation QTc with Bundle Branch Block
< 450 msec	> 500 msec
450 – 480 msec	≥ 530 msec

## 5.5. Subject and Study Completion

A completed subject is one who has completed all phases of the study including all of the follow-up visits.

The date of the end of the study is defined as the date of the last subject's last follow-up visit.

## 6. STUDY TREATMENT

### 6.1. Investigational Product and Other Study Treatment

The term 'study treatment' is used throughout the protocol to describe any combination of products received by the subject as per the protocol design. Study treatment may therefore refer to the individual study treatments or the combination of those study treatments.

Study Treatment		
Product name:	GSK2245035 Nasal Spray Solution 0.2 mcg/mL	Placebo
Formulation description:	A solution formulation in saline preserved with Benzalkonium Chloride and Disodium Edetate	As for GSK2245035 nasal spray solution except for omission of the active ingredient
Dosage form:	Nasal spray solution	Nasal spray solution
Unit dose strength(s)/Dosage level(s):	10 ng per actuation	Not applicable
Route of Administration:	Intranasal Once weekly	Intranasal Once weekly
Dosing instructions:	1 spray per nostril	1 spray per nostril
Physical description:	An amber glass bottle fitted with a screw fit atomizing pump	Visually matched to the active
Device:	Type 1 amber glass bottle fitted with a metered Valois VP7 pump	Type 1 amber glass bottle fitted with a metered Valois VP7 pump
Manufacturer/source of procurement:	GSK	GSK
Method for individualizing dosage:	N/A	N/A

## 6.2. Treatment Assignment

Subjects will be assigned to one of two treatments (either 20 ng GSK2245035 or placebo), in accordance with the randomization schedule generated by Clinical Statistics, prior to the start of the study, using validated internal GSK software RandAll NG. The randomisation will be stratified by centre and also by exposure state during the treatment phase to the allergen selected for BAC (two strata – “Presumed” and “Unknown”). See Section 4.4 for further details regarding allergen exposure.

It is planned that an Interactive Response Technology (IRT) will be used in this study to assign randomization and drug containers. It can also be used to emergency unblind subjects if required (see Section 6.3).

Once assigned to a subject a randomization number may not be re-used.

More details of how and when a subject is allocated a randomization number and the subject numbering convention will be given in the Study Reference Manual (SRM).

### **6.3. Blinding**

This will be a double-blind (sponsor open), study (investigators and subjects are blinded, and sponsor will be unblinded).

During the study, there will be an unblinded interim analysis. Some key GSK study team members may be unblinded as part of this analysis and review. Initially, only the study statistician(s) (and supporting programmers), project physician lead, and medical monitor will be unblinded, and if further data reviews are required then details of who were unblinded to what data and when will be included in the clinical study report.

On-going safety reviews will be conducted during the course of the study in an unblinded manner. Key study team members may be unblinded as part of this review. An external consultant, who is not a GSK employee, may also be unblinded to enable independent review of emerging safety data.

If the GSK medical monitor deems it necessary to unblind data in order to enhance the evaluation of safety and tolerability this will be permitted but also documented and discussed in the clinical study report. The GSK medical monitor will also decide whether to un-blind the investigator(s)/site(s) at that time, or just the sponsor study staff. Details of who were un-blinded to what data and when would then be included in the clinical study report.

Unblinding would occur using the IRT system.

The following will apply.

The investigator or treating physician may unblind a subject's treatment assignment only in the case of an emergency OR in the event of a serious medical condition when knowledge of the study treatment is essential for the appropriate clinical management or welfare of the subject as judged by the investigator.

Investigators have direct access to the subject's individual study treatment.

It is preferred (but not required) that the investigator first contacts the Medical Monitor or appropriate GSK study personnel to discuss options before unblinding the subject's treatment assignment.

If GSK personnel are not contacted before the unblinding, the investigator must notify GSK as soon as possible after unblinding, but without revealing the treatment assignment of the unblinded subject, unless that information is important for the safety of subjects currently in the study.

The date and reason for the unblinding must be fully documented in the CRF.

A subject will be withdrawn if the subject's treatment code is unblinded by the investigator or treating physician. The primary reason for discontinuation (the event or condition which led to the unblinding) will be recorded in the CRF.

GSK's Global Clinical Safety and Pharmacovigilance (GCSP) staff may unblind the treatment assignment for any subject with a Serious Adverse Event (SAE). If the SAE requires that an expedited regulatory report be sent to one or more regulatory agencies, a copy of the report, identifying the subject's treatment assignment, may be sent to investigators in accordance with local regulations and/or GSK policy.

#### **6.4. Packaging and Labeling**

The contents of the label will be in accordance with all applicable regulatory requirements.

#### **6.5. Preparation/Handling/Storage/Accountability**

No special preparation of study treatment is required.

One device is dispensed at dosing visit 1 (to use for the first 4 dose administrations), and a second device will be dispensed at dosing visit 5 (to use for administration of the fifth to eighth doses). Both of these devices will remain in the clinic. All eight doses will be administered to the subjects in the clinic.

The investigator or designee must confirm appropriate temperature conditions have been maintained during transit for all study treatment received and any discrepancies are reported and resolved before use of the study treatment.

Only subjects enrolled in the study may receive study treatment and only authorized site staff may supply or administer study treatment. All study treatments must be stored in a secure environmentally controlled and monitored (manual or automated) area in accordance with the labelled storage conditions with access limited to the investigator and authorized site staff.

The investigator, institution, or the head of the medical institution (where applicable) is responsible for study treatment accountability, reconciliation, and record maintenance (i.e. receipt, reconciliation and final disposition records).

Further guidance and information for final disposition of unused study treatment are provided in the SRM.

Under normal conditions of handling and administration, study treatment is not expected to pose significant safety risks to site staff. Take adequate precautions to avoid direct eye or skin contact and the generation of aerosols or mists. In the case of unintentional occupational exposure notify the monitor, Medical Monitor and/or GSK study contact.

A Material Safety Data Sheet (MSDS)/equivalent document describing occupational hazards and recommended handling precautions either will be provided to the investigator, where this is required by local laws, or is available upon request from GSK.

## **6.6. Compliance with Study Treatment Administration**

When subjects are dosed at the site, they will receive study treatment directly from the investigator or designee, under medical supervision. The date and time of each dose administered in the clinic will be recorded in the source documents. The dose of study treatment and study subject identification will be confirmed at the time of dosing by a member of the study site staff other than the person administering the study treatment.

## **6.7. Treatment of Study Treatment Overdose**

For this study, any dose of GSK2245035 over the stated maximum of the study treatment will be considered an overdose.

GSK does not recommend specific treatment for an overdose. The investigator will use clinical judgment to treat any overdose and provide supportive care as appropriate. The investigator will inform the GSK Medical Monitor immediately, and will document the quantity of the excess dose as well as the duration of the overdosing in the CRF.

Decisions regarding dose interruptions or modifications will be made by the investigator in consultation with the Medical Monitor based on the clinical evaluation of the subject.

## **6.8. Treatment after the End of the Study**

Subjects will not receive any additional treatment from GSK after completion of the study because the indication being studied is not life-threatening or seriously debilitating and other treatment options are available.

The investigator is responsible for ensuring that consideration has been given to the post-study care of the subject's medical condition, whether or not GSK is providing specific post-study treatment.

## **6.9. Challenge Agents**

### **6.9.1. Bronchial, intranasal and intra-dermal allergen challenge/administration**

Appropriate allergen extracts will be purchased by the clinical unit(s) or provided.

The specific allergen extract that will be used for the BAC, NAC and ID challenge will be selected on the basis of each subject's skin prick test. The same allergen will be used for each method of testing. The NAC and ID challenge are not required for eligibility.

A detailed description of how all of the allergen extracts will be selected, the preparation of the allergen extracts and details of the bronchial, intranasal and intradermal allergen challenge techniques can be found in the SRM.

## **6.10. Lifestyle and/or Dietary Restrictions**

### **6.10.1. Meals and Dietary Restrictions**

Dietary restrictions as outlined below will be observed during the time periods specified prior to entry to the clinic and dosing.

### **6.10.2. Caffeine, Alcohol, and Tobacco**

- Subjects will abstain from ingesting excessive amounts (more than one cup) of caffeine- or xanthine-containing products (e.g. coffee, tea, cola drinks, chocolate) for 6 hours prior to each dosing.
- During each visit in the clinic, subjects will abstain from alcohol for 24 hours prior to entry to the clinic until collection of all assessment is completed.
- Subjects will be reminded that all forms of smoking should be avoided during the course of the study.

### **6.10.3. Activity**

Subjects will abstain from strenuous exercise for 48 hours prior to each blood collection for clinical laboratory tests.

Subjects should refrain from all recreational drugs from screening until the final follow-up visit.

## **6.11. Concomitant Medications and Non-Drug Therapies**

### **6.11.1. Permitted Medications and Non-Drug Therapies**

Any concomitant medications not specifically permitted will be considered on a case by case basis by the investigator and GSK medical monitor.

Subjects are permitted to take inhaled short-acting  $\beta$ 2-agonists (SABA) as rescue treatment, but must withhold them for at least 6 hours prior to any study visits with lung function assessment or BAC (screening and follow-up visits 1-3).

Medication to control hypertension is permitted, providing it is anticipated to remain stable from screening to follow up. Beta blockers are not permitted.

Short term use of anti-histamines is permitted with some limitations as outlined in Section 6.11.2; the use of paracetamol and NSAIDS for short-term pain relief is also permitted.

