#### 5.1. Inclusion Criteria

A subject will be eligible for inclusion in this study only if all of the following criteria apply:

AGE
1. Between 18 and 65 years of age inclusive, at the time of signing the informed consent.
TYPE OF SUBJECT AND DIAGNOSIS INCLUDING DISEASE SEVERITY
2. Diagnosis of asthma, as defined by the history of respiratory symptoms such as wheeze, shortness of breath, chest tightness and cough that vary over time and in intensity, together with variable expiratory airflow limitation [ GINA guideline, 2015] for at least 6 months prior to screening. 3. Current asthma therapy. Intermittent short-acting beta-agonist (SABA) alone (on

average for no more than 2 days per week)

4. Positive skin prick test (3mm or more greater than negative control) to common perennial or seasonal aeroallergen(s) (i.e., house dust mite, cat dander, grass pollen) at screening.
5. Pre-bronchodilator FEV1 >70 % predicted normal at Screening Visit 1

NOTE: Predicted values will be based upon [Quanjer](#), 2012.

6. EAR with ≥20 % FEV1 decrease between 5 and 30 minutes after the final allergen concentration is obtained at the screening BAC (decreases relative to the saline).
7. LAR with three FEV1 decreases of ≥15 % between 4 and 10 hours after the final allergen concentration is obtained at the screening bronchial allergen challenge, with two FEV1 decreases being at consecutive time points (decreases relative to the saline).
8. Subjects who are current non-smokers (defined as no use of any tobacco products in the 6-month period preceding the screening visit) and have a pack history of < 10 pack years

Number of pack years = (number of cigarettes per day/20) x number of years smoked

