## 7. STUDY ASSESSMENTS AND PROCEDURES

Protocol waivers or exemptions are not allowed with the exception of immediate safety concerns. Therefore, adherence to the study design requirements, including those specified in the Time and Events Table, are essential and required for study conduct.

This section lists the procedures and parameters of each planned study assessment. The exact timing of each assessment is listed in the Time and Events Table Section [7.1](#)

The following points must be noted:

- If assessments are scheduled for the same nominal time, THEN the assessments should occur in the following order:

1. 12-lead ECG
2. vital signs
3. blood draws.

Note: The timing of the assessments should allow the blood draw to occur at the exact nominal time.

- The timing and number of planned study assessments, including safety, pharmacokinetic, pharmacodynamic/biomarker assessments may be altered during the course of the study based on newly available data to ensure appropriate monitoring. Similarly the timing of the post-treatment allergen challenges may change based on new information acquired during the course of the study.
- Details of the order of planned assessments for each visit and the time windows around these visits and assessments will be given in the SRM.
- The change in timing or addition of time points for any planned study assessments must be documented in a Note to File which is approved by the relevant GSK study team member and then archived in the study sponsor and site study files, but this will not constitute a protocol amendment.

- The Institutional Review Board (IRB)/Independent Ethics Committee (IEC) will be informed of any safety issues that require alteration of the safety monitoring scheme or amendment of the Informed Consent Form.
- No more than 500 mL of blood will be collected over the duration of the study, including any extra assessments that may be required.

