## 7.1. Time and Events Tables

### 7.1.1. Time and Events Table – Screening Visit(s)

Procedure	Screening Visit 1 (up to Day -28)	Screening Visit 2 (up to Day -3))	24 hours after Screening Visit 2 (Day -20 to Day -2)	Notes
Informed consent signing	X			Includes genetics consent
Inclusion and exclusion criteria/eligibility review	X	X		
Demographics	X			
Medical history (including substance usage and family history of premature CV disease)	X			
Past and current medical conditions including cardiovascular medical history	X			
Concomitant medication review	X			
Full physical exam including height and weight	X			
Urine drug/alcohol screen	X			
Urine or serum pregnancy test (all females)	X			No women of childbearing potential are being enrolled. However this test is needed to confirm pregnancy status at screening.
Serum FSH and estradiol for post-menopausal females	X			
HIV, Hep B and Hep C screen	X			
Laboratory assessments (including liver chemistries, haematology, clinical chemistry and urinalysis)	X			
Screening Spirometry assessment	X			To confirm $FEV_1 > 70\% \text{ predicted}$
SAE Collection	X	X	X	
12-lead ECG	X			
Vital signs	X			
Skin prick test	X			To confirm eligibility
FeNO measurement	X		X	Collected prior to sputum induction
Saline and incremental BAC challenge plus associated spirometry measurements		X		Including pre-procedure $FEV_1$ assessment and repeat $FEV_1$ measurements up to 10 hours post BAC

Procedure	Screening Visit 1 (up to Day -28)	Screening Visit 2 (up to Day -3))	24 hours after Screening Visit 2 (Day -20 to Day -2)	Notes
Sputum induction and processing for BAC associated sample collection	X		X	There must be a minimum of 48 hours between 'Screening Visit 1' and 'Screening Visit 2'. This ensures adherence to a minimum 3-day window between sputum inductions. There must be a minimum of 48 hours between '24 hours after Screening Visit 2' and 'Dosing Visit 1'
Laboratory assessments (haematology only)		X	X	Blood samples should be taken pre-BAC on SV2 and on the following day at 24 hrs post BAC
Blood samples for PBMC preparations		X		Blood samples for PBMC preparations (pre-BAC and 6 hours after BAC at screening visit 2)
Provide diary card, PEF meters, rescue medication and thermometers to subjects		X		Only given out to subjects who are eligible following the BAC. Thermometers are to be given to record temperature as part of capturing AE information.

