### 7.1.3. Time and Events Table – Follow up visits (FUV1 to 3) (Weeks 9 to 20)

Procedure	Follow up Visit 1 (FUV1)		Follow-up Visit 2 (FUV2)			2 month follow-up phone call (Week 16)	Follow up Visit 3 (FUV3)			Notes	
	Week 9 (1 week after DV8)	24 hours later	Week 11 (3 weeks after DV8)	Week 12 (4 weeks after DV8)	24 hours later		Week 19 (11 weeks after DV8)	Week 20 (12 weeks after DV8)	24 hours later		
AE/SAE review	<=====>			X 	<=====>						
Concomitant medication review	<=====>			X 	<=====>					 Phone call made to the subject to check AEs and concomitant medications and confirm availability for FUV3	
Diarycard collection, review and dispensing	X									Review diary card at every visit until the end of FUV 2	
FeNO measurement	X	X		X	X			X	X	Collect prior to sputum induction	
Blood sample for RNA analysis				X						PAX tubes for /AFFY chip gene expression in blood. Collected prior to the bronchial allergen challenge at FUV2	
Saline and bolus BAC challenge plus associated spirometry measurements	X			X				X		Including pre-procedure FEV 1 assessment and repeat FEV 1 measurements up to 10 hours post BAC	
Sputum induction and processing for BAC associated sample collection		X	X		X		X		X	Sputum induction pre-BAC and 24 hours after BAC	
Laboratory assessments (haematology only)	X	X		X	X		X 	X		Blood samples should be taken pre-BAC and on the following day at 24hrs post BAC	
Blood samples for PBMC preparations	X			X				X		Blood samples for PBMC preparations (pre-BAC and 6 hours after BAC)	

Procedure	Follow up Visit 1 (FUV1)		Follow-up Visit 2 (FUV2)			2 month follow-up phone call (Week 16)	Follow up Visit 3 (FUV3)			Notes
	Week 9 (1 week after DV8)	24 hours later	Week 11 (3 weeks after DV8)	Week 12 (4 weeks after DV8)	24 hours later		Week 19 (11 weeks after DV8)	Week 20 (12 weeks after DV8)	24 hours later	
Nasal lavage		X			X					Collect nasal lavage to provide a background sample. Repeat nasal lavage pre-NAC, then again 5 minutes and at least 6 hours post-NAC.
Nasal filter collection		X			X					Collect nasal filter sample to provide a background pre-wash sample, after nasal wash repeat nasal filter sampling pre-NAC, then again 5 minutes and at least 6 hours post-NA.
NAC		X			X					Commence after the 24-hour BAC sputum and blood biomarker samples have been taken at FUV1 and FUV2

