**REVISED TEXT**

Any concomitant medications not specifically permitted will be considered on a case by case basis by the investigator and GSK medical monitor.

Subjects are permitted to take inhaled short-acting  $\beta$ 2-agonists (SABA) as rescue treatment, but must withhold them for at least 6 hours prior to any study visits with lung function assessment or BAC (screening and follow-up visits 1-3).

Medication to control hypertension is permitted, providing it is anticipated to remain stable from screening to follow up. Beta blockers are not permitted.

**Section 6.11.2 Prohibited Medications and Non-Drug Therapies. Clarification around the time period for which drugs are not permitted is provided.**

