1 REPORTING & ANALYSIS PLAN SYNOPSIS

Overview	Key Elements of the RAP
Purpose	
 To describe the planned efficacy, biomarker/pharmacodynamics, safety, and pharmacokinetics analyses and output to be included in the Clinical Study Report.
Protocol	
 This RAP is based on the Protocol Amendment 2 (Dated: 17/AUG/2016) of Study 205540 (GSK Document No.: 2015N264314_02) and eCRF Version 2.
Primary Objective	
 To evaluate the effect of treatment with i.n. GSK2245035 20 ng once weekly (qw) compared to placebo on the allergen-induced late asthmatic response (LAR) in subjects with allergic asthma.
Primary Endpoint	
 LAR: minimum FEV₁ between 4-10 hours following allergen challenge one week after treatment. LAR: weighted mean (WM) FEV₁ between 4-10 hours following allergen challenge one week after treatment.
Study Design	
 Randomised (stratified by centre and allergen exposure ('presumed'/'unknown')), double-blind (sponsor open), placebo-controlled, parallel group, 8-week treatment in mild allergic asthmatics
Planned Analyses	
 The planned Interim analysis is detailed within Section 3.1 (including details of sample size adjustment). Pre-Database Freeze (DBF) headline data using FUV1 FEV1 BAC challenge results will be produced for internal GSK review/decision making but these outputs will not be formally reported, since they will be superseded by the final analysis. All decisions regarding final analysis, as defined in this RAP document, will be made prior to DBF of the study data.
Analysis Populations	
 Primary analysis: Per-Protocol Population (comprised of subjects who receive at least one dose of study treatment and commence a BAC at follow-up, i.e. mITT subjects who are not major protocol violators). Modified Intent-To-Treat Population / Safety / Sputum Producers & PK are other analysis populations that would be used (See Section 4) for full details

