- If an observation is missing between two non-missing observations, the AUC will be linearly interpolated between the two non-missing values i.e., the subject's profile will be assumed to be linear between the two available values. No imputation will be made if either the first or last observation is missing.
- If the number of missing values is considered to be substantial, or if the data is not considered to be missing at random, a sensitivity analysis will be carried out with respect to methods of handling missing data in the calculation of the weighted mean.
- The weighted mean will be set to missing for the relevant challenge if any of the following occurs:
 - A short-acting inhaled β -agonist is taken within 8 hours at any time prior to the challenge
 - The dose of allergen administered is different to that of the Screening dose. Note that the dose of allergen used during the treatment period may be modified from the total dose received at screening, for safety reasons, at the discretion of the investigator. However, in this case, the modified dose used must be consistent for all follow up visits. [In these cases the baseline will be set to missing.]
 - The weighted mean LAR will be set to missing if the subject took rescue medication prior to the LAR period i.e., between 0 and 4 hours post-saline.
 - If rescue medication is administered during the LAR period prior to the completion of the 10 hour FEV_1 assessment, all FEV_1 values recorded after the administration of rescue medication for that challenge will be set to the last recorded FEV_1 value prior to the administration of rescue medication. The LAR does not have the same natural recovery as the EAR, hence this is the most appropriate derivation for the LAR. The weighted mean LAR will then be calculated as above, using the imputed data set.
 - If the use of rescue medication is widespread and/or appears to follow a trend, appropriate sensitivity analyses to examine the impact of the derivations may be conducted. For example, if a large number of subjects are rescued at around 8 hours, the weighted mean LAR over 4-8 hours may be derived and analysed as a sensitivity analysis. All sensitivity analyses will be documented in the CPSR.
 - There may be other conditions that effect the LAR response. In such situations it may be necessary to set the respective response to missing. Such scenarios will be

LAR and EAR

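### A patient who obeys the protocol's 6-hour SABA rule can still have both primary LAR results set to missing by the SAP's 8-hour rule; the expected loss is small and may be zero

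*Protocol*

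**What the plan says.** Protocol 6.11.1 (Permitted Medications) lets patients use inhaled SABA as rescue, but they "must withhold them for at least 6 hours prior to any study visits with lung function assessment or BAC". It names screening and follow-up visits 1 to 3. The interval is counted to the visit.

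SAP 11.5.4 (Efficacy) lists conditions under which an LAR endpoint is set to missing for a challenge. One of them is that a short-acting inhaled beta-"agonist is taken within 8 hours at any time prior to the challenge". It appears twice, once for weighted mean LAR and once for minimum LAR. These are the two primary endpoints, and SAP 7.1.2 models each separately. The interval is counted to the challenge.

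This is not a matter of superseded text. The SAP synopsis says "This RAP is based on the Protocol Amendment 2", and the revised text of that amendment (Protocol 12.7) already reads "but must withhold them for at least 6 hours prior to any study visits with lung function assessment or BAC". The current protocol keeps the rule.

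**The concern.** The two rules use different lengths (6 and 8 hours) and different end points (visit and challenge). A patient can satisfy the first and fail the second. That patient goes through an allergen challenge and at least 10 hours of monitoring (Protocol 4.6.1), and both primary results are then discarded. The 8-hour limit does not appear in the protocol, so a site working from it has no prompt to delay the start.

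Nothing later in the SAP brings the FUV1 value back. It is blanked when the endpoint is derived, so the mITT sensitivity analysis (SAP 7.1.1) does not contain it either. The missing-at-random handling (SAP 11.6.2.3) and the repeated-measures check (SAP 8.1.2) can use the patient's other visits, but they do not restore the observation.

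The same wording could blank the Screening Visit 2 baseline. SAP 7.1.2 then drops that patient from the model, although SAP 11.6.2.3 allows imputation case by case.

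**Working it through.** **1. The plan's own figure, used only to price a lost patient.** Protocol 9.2.1 gives success probabilities of about 78% (minimum LAR) and 81% (weighted mean LAR) with 20 completers per arm. Inputs: the posterior threshold of 0.7 and the 18% and 27% attenuations (Protocol 9.2), and the eight studies in Table 2. I take the unweighted mean placebo response and the median residual variability, read as a variance V.

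Success probability = 1 − F(t; 2n − 2, λ), where F is the noncentral t distribution function, t is the 0.7 quantile of the central t on 2n − 2 degrees of freedom, and λ = δ / √(2V/n).

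- Minimum LAR: δ = 0.18 × 1.0504 = 0.189 L, V = 0.218. Result: 77.45% at n = 20 and 76.46% at n = 19.
- Weighted mean LAR: δ = 0.27 × 0.6558 = 0.177 L, V = 0.151. Result: 81.93% at n = 20 and 80.95% at n = 19.

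Both values at n = 20 are within 1 point of the protocol. One patient lost per arm costs about 1 point. Weighting Table 2 by degrees of freedom gives 76.8% and 81.0% at n = 20, then 75.9% and 80.0% at n = 19, so the price is the same.

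**2. Both rules on one clock.** Let s be the hours from last SABA to arrival and c the hours from arrival to challenge.

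- Complies with the protocol: s ≥ 6.
- Set to missing by the SAP: s + c < 8.
- Both at once: 6 ≤ s < 8 − c, an exposed window of g = 2 − c hours.

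If c = 0.5, the exposed range is 6 to under 7.5 hours. If c = 1, it is 6 to under 7. If c = 1.5, it is 6 to under 6.5. If c ≥ 2, there is none.

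The value of c is not in the documents, but it is above zero. The follow-up table (Protocol 7.1.3) requires pre-challenge blood ("Blood samples should be taken pre-BAC and on the following day at 24hrs post BAC"), a pre-procedure FEV1 and saline before the allergen. The rest is left to the Study Reference Manual: "Details of the order of planned assessments for each visit and the time windows around these visits".

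**3. Expected loss at FUV1.** The documents give no SABA rate, so the floor is zero. Assumptions: u = 1 to 2 uses a week, at random times, one use per SABA day. The upper value equals the per-protocol limit of 2 days a week on average (SAP 11.1.1). The illustrative window is g = 1 hour.

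Loss per challenge: p = 1 − exp(−u × g / 168).

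- u = 1: p = 0.00593. Of 40 patients, 40p = 0.24 are lost (0.12 per arm). The chance of at least one is 1 − (1 − p)^40 = 21.2%.
- u = 2: p = 0.01183. Of 40 patients, 40p = 0.47 are lost (0.24 per arm). The chance of at least one is 37.9%.

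**4. Cost in success probability.** At about 1 point per patient lost per arm, 0.12 to 0.24 patients per arm cost about 0.12 to 0.24 points.

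**The case against.** The strongest reply is that the harm turns on a document nobody here can see. The manual may schedule 2 hours of procedures before allergen, or state its own SABA interval, and then nothing is lost. This stands as a limit on the size. It does not remove the conflict, because neither supplied document requires 2 hours between arrival and challenge.

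A second reply is that the rules need not match: one is a minimum for patient conduct, and the other decides whether an FEV1 series can be evaluated, which may fairly be stricter. This stands in part. Neither document explains 6 or 8 hours, so neither can be called wrong. A stricter evaluability rule still needs an instruction that lets a site meet it.

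Third, use at random times probably overstates exposure. Monitoring of at least 10 hours suggests a morning start, which would put the gap overnight. No clock time is given, so this is inference, but it points to a smaller loss. Two uses a week for every patient is also a ceiling.

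A reader might infer that the full 2-hour gap is exposed. It cannot be, since that would need the challenge to start on arrival.

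**Conclusion.** The conflict between the two rules is certain on the text, and it reaches both primary endpoints. Its consequence is minor. For a 1-hour window and 1 to 2 SABA uses a week at random times, the expected loss is about 0.2 to 0.5 of 40 patients, up to about 0.24 per arm. The chance of losing at least one patient is about 21% to 38%, and the fall in success probability is about a quarter of a point or less. The window and the SABA rate are assumptions, and the true loss may be zero.

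Two stronger readings are not supported. One is that the sample size is threatened: a quarter of a point against 78% and 81% does not show that. The other is that the treatment comparison is biased. SABA use shortly before a challenge may reflect recent symptoms, so missing at random is open to question for such a patient, but nothing in the documents shows a difference between arms. The reason to act is that the loss is avoidable by aligning one interval.

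**What to change.** Use one interval in both documents. The sponsor should choose between two options.

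- **Change the protocol.** State in 6.11.1 that SABA must be withheld for at least 8 hours before the allergen challenge at Screening Visit 2 and FUV1 to FUV3. Keep 6 hours for visits with lung function but no challenge, such as Screening Visit 1 ("Screening Spirometry assessment" in Protocol 7.1.1). Sites check the last SABA time before saline and, if needed, delay the start the same day. A patient who met the 6-hour rule reaches 8 hours no later than 2 hours after arrival. The cost is a minor amendment with ethics review as applicable, a slightly longer wash-out, and occasionally a clinic day up to 2 hours longer. On the assumptions above, if SABA habits do not change, that is 160p = 0.9 to 1.9 of 160 challenges (40 patients, four challenges each).
- **Change the SAP**, if the sponsor considers 6 hours sufficient. In 11.5.4, for both weighted mean and minimum LAR, set the endpoint to missing only if SABA was taken within 6 hours before the visit. Nothing changes for patients or sites. The cost is that FEV1 data are kept from patients who took SABA 6 to 8 hours before the challenge.

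In either case, check that the Study Reference Manual states the same interval.
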